Following signing of IRB-approved informed consent, screening, and acceptance by an Enrollment Authorization Committee, subjects in each cohort who meet entry criteria will present to the clinic on the morning of Day 1 in the practically defined OFF state (having withheld anti-parkinsonian medications after 10:00 PM the evening prior). Prior to dosing on Day 1, Subjects will be randomized to either placebo or BTRX-246040. Subjects will then be dosed with study drug and UPDRS Part III motor response, dyskinesia rating and ON/OFF status will be assessed pre-dose and every 30 minutes for 4 hours and then hourly for 4 additional hours (i.e., 8 hours total post-dose). Subjects who turn ON following study drug administration, and remain ON after 8 hours, should be called the next morning to record the time they turned OFF and took their first regularly scheduled anti-parkinsonian medications after study drug, to a maximum of 24 hours.

On Day 1 subjects will come to clinic in a fasted state and will be administered a standard low protein breakfast. [REDACTED]

Subjects who reach and remain in the ON state for 8 hours will resume their regularly scheduled anti-parkinsonian medications 8 hours post-dosing. Subjects should remain on study drug until they experience an OFF episode after a full ON for 8 hours. However, if after 4 hours post study drug dosing, a subject's motor symptoms are severe and not responsive to study drug, the subject's regularly scheduled levodopa dose and other anti-parkinsonian medications may be administered, if deemed necessary based on the judgment of the investigator. All subjects, whether they are administered their regularly scheduled anti-parkinsonian medication or not will continue with study procedures until the end of the observation period of 8 hours. Orthostatic vital signs will be assessed pre-dose and 2, 4, 6, and 8 hours after dosing.

Subjects will return to the clinic 7 days later (Day 8) for a follow-up safety visit.

Following completion of cohorts 1 and 2, a Dosing Review Committee (DRC) meeting will take place to review available unblinded safety, tolerability, efficacy and, if available, PK data and determine if it is safe to go up to the next higher dosage for the next cohort. At any point, the DRC can request that a dosage be repeated for safety or tolerability rather than increased.

Inclusion Criteria

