Placebo will be administered orally at the same number of capsules as active drug at each Cohort. Placebo capsules will consist of inactive ingredients and look identical to BTRX-246040.

Planned Duration of Treatment:

Study drug will be administered once on Day 1

Criteria for Evaluation:

Safety: Will be assessed descriptively by adverse events reporting which will include AEs, SAEs, vital signs, laboratory values, physical and neurological exams, C-SSRS, and ECGs.

Tolerability: Will be assessed by percent who complete protocol

Pharmacokinetics: Descriptive review of Pharmacokinetic (PK) ██████████
███████████

Efficacy: Will be assessed descriptively for the following endpoints.

Primary Endpoint:

- Maximal change in UPDRS Part III from pre-dose to post-dose on Day 1

Secondary Endpoints:

- Duration of ON time on Day 1
- Percentage of subjects that turn ON on Day 1
- Time to ON on Day 1

- Area under the curve for UPDRS Part III during the 8 hours of assessment on Day 1
- Change from pre-dose dyskinesia rating (from the UPDRS Part III motor response and dyskinesia assessment)

Statistical Methods:

All data will be assessed descriptively as presented in the SAP, and no formal statistical comparisons will be performed.

Sample Size Calculation:

Formal sample size calculation will not occur. A sample size of 8 subjects per group is deemed sufficient to evaluate the preliminary safety, tolerability, and efficacy of the different dose levels.

TABLE OF CONTENTS

1	Synopsis.....	2
Table of Contents.....		8
2	Protocol Signature Page.....	14
3	Abbreviations.....	15
4	Introduction	18
5	Objectives.....	21
5.1	Primary Objective	21
6	Investigational Plan.....	22
6.1	Summary of Study Design	22
6.2	Study Design and Control.....	23
7	Study Population	24
7.1	Inclusion Criteria.....	24
7.2	Exclusion Criteria.....	25
7.2.1	Rationale for Exclusion of Certain Subjects	27
7.3	Discontinuations	27
7.3.1	Early Discontinuation.....	27
7.3.2	Discontinuation of the Study.....	28
8	Study Procedures.....	29
8.1	Visit 1: Screening.....	29
8.2	Visit 2: Treatment Period (Day 1).....	30
8.3	Visit 3: Safety Follow-up (Day 8 ±1)	31
8.4	Early Termination Visit	32
9	Treatment.....	33
9.1	Treatments Administered.....	33

9.2 Materials and Supplies.....	33
9.3 Method of Assignment to Treatment.....	33
9.4 Rationale for Selection of Doses in the Study.....	33
9.5 Selection and Timing of Doses.....	34
9.6 Blinding	35
9.7 Dosing Review Committee	35
9.8 Concomitant Therapies.....	35

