6 INVESTIGATIONAL PLAN

6.1 SUMMARY OF STUDY DESIGN

The study will consist of 3 sequential, ascending dose cohorts of 8 subjects each with a 6:2 randomization to BTRX-246040 or placebo. The planned dosing for each cohort will be 40, 80, and 120 mg. After enrollment of the first cohort has been completed, doses for subsequent cohorts may be modified based on review of the available data (safety, tolerability, efficacy, and PK) by an unblinded Dosing Review Committee (DRC). A similar review and determination of dosing for the subsequent cohort will be performed after completion of cohorts 1 and 2 and based on all data available from previous cohorts.

Following screening and acceptance by an Enrollment Authorization Committee, subjects in each cohort who meet entry criteria and sign an IRB approved informed consent, will present to the clinic on the morning of Day 1 in the practically defined OFF state (having withheld anti-parkinsonian medications after 10:00 PM the evening prior). Prior to dosing on Day 1, subjects will be randomized to either placebo or BTRX-246040. Subjects will then be dosed with study drug and UPDRS Part III motor response, dyskinesia and ON/OFF status will be assessed pre-dose and every 30 minutes for 4 hours and then hourly for 4 additional hours (i.e., 8 hours total post-dose). Subjects who turn ON following study drug administration and remain ON after 8 hours, should be called the next morning to record the time they turned OFF and the time they took their first regularly scheduled anti-parkinsonian medications after study drug, to a maximum of 24 hours. Subjects who turn ON following study drug administration and subsequently turn OFF may be administered their regularly scheduled levodopa dose and other anti-parkinsonian medications.

Subjects who

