reach and remain in the ON state for 8 hours may resume their regularly scheduled anti-parkinsonian medications 8 hours post-dosing. Subjects should remain on study drug until they experience an OFF episode after a full ON for 8 hours. However, if after 4 hours post study drug dosing, a subject's motor symptoms are severe and not responsive to study drug, the subject's regularly scheduled levodopa dose and other anti-parkinsonian medications may be administered, if deemed necessary based on the judgment of the investigator. All subjects, whether they are administered their regularly scheduled anti-parkinson medication or not will continue with study procedures until the end of the observation period of 8 hours.

Subjects will come to clinic in a fasted state and will be administered a standard low protein breakfast.

Orthostatic vital signs will be assessed pre-dose and 2, 4, 6, and 8 hours after dosing.

Subjects will return to the clinic 7 days later (Day 8) for a follow-up safety visit.

Following completion of cohorts 1 and 2, a Dosing Review Committee (DRC) meeting will take place to review available unblinded safety, tolerability, efficacy and, if available, PK data and determine if it is safe to go up to the next higher dosage for the next cohort. At any point the DRC can request that a dosage be repeated.

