7.1 INCLUSION CRITERIA

Subjects are eligible to be included in the study only if they meet **all** the following criteria:

1. Diagnosed with Parkinson's disease (consistent with the UK PD Society Brain Bank Criteria for the Diagnosis of PD)
2. Men or women ≥ 30 years old and ≤ 76 years old
3. Female subjects must be either surgically sterilized or 2 years post menopausal at screening
4. Modified Hoehn and Yahr scale ≤ 3 in the ON state
5. Montreal Cognitive Assessment (MoCA) Score ≥ 26
6. Currently has a clear and decisive response to levodopa, and receiving a stable dose of levodopa (at least 4 doses per day of levodopa or ≥ 3 doses per day of RytaryTM (Carbidopa and levodopa Extended-Release Capsules) for at least four weeks prior to screening)
7. Experiencing motor fluctuations during waking hours with at least 2 hours of OFF periods each day, including predictable early morning OFF periods, based on subject assessment
8. Able to participate in the study in the practically defined OFF state
9. All anti-parkinsonian medications maintained at a stable dose for at least 4 weeks prior to the initial Screening Visit with the exception of MAO-B inhibitors, which must be maintained at a stable level for at least 8 weeks prior to the screening visit
10. Approved by a central Enrollment Authorization Committee as meeting entry criteria and being a suitable candidate for the study
11. Male subjects agree to use a reliable method of birth control during the study and for at least 90 days following the last dose of BTRX-246040 or placebo.
12. Informed and given ample time and opportunity to think about his/her participation in this study and has given his/her written informed consent on an Institutional Review Board (IRB) or Independent Ethics Committee (IEC) approved consent form
13. Judged to be reliable and able to keep all appointments for clinic visits, tests, and procedures, including venipuncture, and examinations required by the protocol.

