8.2 VISIT 2: TREATMENT PERIOD (DAY 1)

For each cohort, subjects approved by the EAC for further participation in the study will return to the clinic within 28 days of the screening visit on the morning of Day 1, in the practically defined OFF state (having not taken any anti-PD medications since 10 PM the evening before).

Subjects will come to clinic in a fasted state and will be administered a standard low protein breakfast. Subjects will be randomized to either BTRX-246040 or placebo.

In the clinic, subjects determined to be in the OFF state by the Investigator will be dosed with study drug and UPDRS Part III motor response and dyskinesia rating, and ON/OFF status will be assessed pre-dose and every 30 minutes post-dose for 4 hours, and then hourly for an additional 4 hours (i.e., 8 hours total post-dose). Time to ON and duration of ON, if applicable, will also be recorded.

Subjects who reach and remain in the ON state for 8 hours may resume their regularly scheduled anti-parkinsonian medications 8 hours post-dosing. Subjects should remain on study drug until they experience an OFF episode after a full ON for 8 hours. However, if after 4 hours post study drug dosing, a subject's motor symptoms are severe and not responsive to study drug, the subject's regularly scheduled levodopa dose and other anti-parkinsonian medications may be administered, if deemed necessary based on the judgment of the investigator. All subjects whether they are administered their regularly scheduled anti-parkinsonian medications or not, will continue with study procedures until the end of the observation period of 8 hours.

The following assessments will be completed on Day 1 - see the Schedule of Assessments ([Appendix 1](#)) for details:

1. Collection of concomitant medications

2. Vital Signs: (BP and pulse both supine and standing, respiratory rate, temperature) and weight. Three sets each of supine and standing BP and pulse rate will be measured at least 15-20 minutes apart at pre-dose and will be measured once at 2, 4, 6, and 8 hours after dosing
3. C-SSRS – since last visit version
4. QUIP-RS – since last visit version
5. 12-lead ECG pre-dose and 1 hour after study drug administration.
6. Randomization via IWRS

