12.2.7.1 PRIMARY EFFICACY ANALYSIS

The maximal change from predose in UPDRS Part III scores will be summarized by data listings, descriptive statistics, and graphical displays. This analysis will use the mITT Population.

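### The maximal UPDRS Part III change and the other Day 1 endpoints do not stop at levodopa given within the 8 hours, so a levodopa response can be reported as the primary result

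*Protocol*

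**What the plan says.** The Synopsis defines the primary endpoint as "Maximal change in UPDRS Part III from pre-dose to post-dose on Day 1". Section 12.2.7.1 adds only how it will be presented, in the mITT Population: "The maximal change from predose in UPDRS Part III scores will be summarized by data listings, descriptive statistics, and graphical displays". Section 12.2.7.3 lists duration of ON, percentage turning ON, time to ON, UPDRS Part III AUC over the full 8 hours, and change in dyskinesia rating. None is tied to the time of an anti-parkinsonian dose. Section 12.2.7.2 rules out any sensitivity analysis of the primary endpoint.

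The same protocol allows such doses inside the window:

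- **After 4 hours, non-responders (Synopsis, 6.1, 8.2).** For a subject whose "motor symptoms are severe and not responsive to study drug", the "regularly scheduled levodopa dose and other anti-parkinsonian medications may be administered, if deemed necessary based on the judgment of the investigator".
- **After ON then OFF (6.1 only, no earliest time).** "Subjects who turn ON following study drug administration and subsequently turn OFF may be administered their regularly scheduled levodopa dose and other anti-parkinsonian medications".
- **Ratings go on.** Subjects, medicated or not, "will continue with study procedures until the end of the observation period of 8 hours" (8.2; same rule in the Synopsis and 6.1).
- **Population (7.1, criterion 6).** "Currently has a clear and decisive response to levodopa, and receiving a stable dose of levodopa".
- **At 8 hours.** The Synopsis says subjects still ON "will resume their regularly scheduled anti-parkinsonian medications 8 hours post-dosing"; 6.1 and 8.2 make this optional. Their ON time is followed by telephone to 24 hours.

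The nearest thing to a stopping rule is footnote 5 of Appendix 1, which lets the hourly ratings end once a subject is OFF. It is tied to OFF status, not to medication, and it conflicts with the rule that procedures run to 8 hours.

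**The concern.** A maximum is set by the single best rating. The subjects eligible for levodopa after 4 hours are those judged not to respond to study drug, and by the entry criteria they respond to levodopa. Followed as written, the plan can therefore take the worst study-drug outcomes and record them among the best.

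The direction of the error depends on who is treated. Levodopa given to non-responders raises the mean of whichever arm receives more of it. If that is placebo, a real drug effect shrinks or disappears. Levodopa given after ON then OFF flatters the active arm when the drug works, provided ratings continue after OFF.

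Each cohort has 6 active and 2 placebo subjects, 6 placebo subjects over three cohorts, so one treated subject moves a mean visibly. Under section 9.7 the Dosing Review Committee may modify later doses after a review that includes efficacy.

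**Working it through.** The protocol has no figure to reproduce: no power, effect size, rating SD or expected rate of levodopa use.

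**1. Exposure, from the rating schedule.** Post-dose ratings fall at 0.5 to 4 h in half-hour steps (8) and at 5, 6, 7 and 8 h (4), 12 in all. For levodopa given just after the 4 h rating:

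- ratings affected: 4/12 = 33%
- AUC hours affected: (8 − 4)/8 = 50%

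**2. One non-responder.** Assumed: independent rating error with SD 3, no study-drug benefit, levodopa just after 4 h, levodopa benefit present from 5 h to 8 h. Maximal change = pre-dose score − lowest post-dose score. In a simulation of 400,000 subjects per arm, rating error alone gives a mean maximal change of 4.9. With a levodopa benefit of 15 it is 4.9 + 13.2 = 18.1, and a post-levodopa rating sets the maximum in over 99% of cases.

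| Levodopa benefit | Rise in maximal change | Shift in a mean of 6 (rise/6) | Shift in a mean of 2 (rise/2) |
|---|---|---|---|
| 10 | 8.2 | 1.4 | 4.1 |
| 15 | 13.2 | 2.2 | 6.6 |
| 20 | 18.2 | 3.0 | 9.1 |

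**3. Active-placebo difference.** Further assumed: drug benefit of 8 points from 1 h in active subjects not given levodopa, none in those given it, and no placebo improvement. Then

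all-ratings difference = no-levodopa difference − rise × (placebo share treated − active share treated).

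For 67%/33% and benefit 15: 5.3 − 13.2 × 0.34 = 0.8.

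| Placebo/active treated | No levodopa | All ratings, benefit 10 | All ratings, benefit 15 | All ratings, benefit 20 | Cut at first dose, benefit 15 |
|---|---|---|---|---|---|
| 25%/10% | 7.1 | 5.9 | 5.1 | 4.4 | 7.2 |
| 33%/17% | 6.5 | 5.2 | 4.4 | 3.6 | 6.6 |
| 50%/50% | 3.9 | 3.9 | 3.9 | 3.9 | 3.9 |
| 67%/33% | 5.3 | 2.5 | 0.8 | −0.9 | 5.5 |
| 80%/40% | 4.7 | 1.4 | −0.6 | −2.6 | 5.0 |

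Rerunning the simulation reproduces these within 0.1. At 50%/50% the difference is unbiased but the placebo mean rises to 4.9 + 0.5 × 13.2 = 11.5. With a 3-point placebo improvement in both arms and benefit 15, the all-ratings differences are 5.6, 5.0, 4.0, 1.8 and 0.7, against 7.2, 6.6, 4.0, 5.4 and 4.8 without levodopa.

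The unbiased 50%/50% row depends on treated active subjects having no drug benefit. A second simulation let all active subjects keep a 5-point drug benefit (levodopa 15, change-score SD 4, levodopa benefit at 5 to 7 h). At 50%/50% the active advantage falls to 2.5, against 5.0 with the cut. At 67%/33% the active arm looks worse by 1.0, against an advantage of 5.2 with the cut.

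**4. AUC difference in point-hours (assumptions of step 3, benefit 15).**

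| Placebo/active treated | 0-8 h, no levodopa | 0-8 h, all ratings | 0-4 h |
|---|---|---|---|
| 25%/10% | −52 | −44 | −23 |
| 33%/17% | −48 | −40 | −22 |
| 50%/50% | −29 | −29 | −13 |
| 67%/33% | −39 | −21 | −17 |
| 80%/40% | −35 | −14 | −16 |

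Levodopa given after 4 h leaves the 0-4 h column unchanged.

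**5. ON-then-OFF route alone (benefit 15, ratings continuing after OFF).** With 17% of active subjects treated this way, 7.7 becomes 8.8; with 33%, 7.6 becomes about 9.6. Cutting at the dose returns 7.7 and 7.6.

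**6. Not simulated.** Percentage ON and time to ON are affected only in subjects who first turn ON after levodopa. Duration of ON can run on under medication resumed at 8 h.

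**The case against.** The strongest reply is that handling of ratings after levodopa is a derivation rule that a SAP may supply. The protocol refers to a SAP, which was not available for this review, and a SAP could define the primary value on pre-levodopa ratings without contradicting 12.2.7.1. That possibility remains. But this is more than silence: the protocol sets the window at Day 1 post-dose, fixes the AUC at 8 hours, orders ratings to continue after levodopa, and excludes the sensitivity analysis that would show the effect.

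Several other points stand in part:

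- The study is descriptive, so no type I error is at stake. Listings and time-point plots would show the pattern, and ratings to 4 h are free of levodopa under the non-responder route. The primary summary itself still would not separate drug from levodopa.
- The committee decisions listed in 9.7 that give a reason cite toxicity or safety, and 10.5.8 describes a review of safety and tolerability. Efficacy is nevertheless named in 9.7 among the data on which doses may be modified.
- For subjects still ON at 8 h, the time of the first anti-parkinsonian dose is already recorded. That makes the fix cheaper.
- Dosing just after 4 h is the worst case for that route; later dosing affects fewer ratings.
- A 0-4 h AUC discards half the window, so its difference is smaller by construction. It complements the 8-hour AUC, which remains a mixture of drug and levodopa.

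**Conclusion.** The concern holds and should be fixed before the primary endpoint is summarised. The textual conclusion needs no assumption: a levodopa response in a study-drug non-responder can be that subject's primary result.

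The size rests on assumed inputs. The per-subject rise of about 8 to 18 points needs only a levodopa benefit of 10 to 20 points and dosing just after 4 h. The effect on the active-placebo difference also needs treatment rates: about 1 to 3 points lost at modest unequal rates (25%/10% or 33%/17%), most or all of the difference lost at 67%/33% or 80%/40% with a benefit of 15. Reversal of sign under the main assumptions needs heavy, unequal use and a levodopa response well above the drug effect. The ON-then-OFF route matters only if the 8-hour rule, not footnote 5, governs the ratings.

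**What to change.** Amend the Synopsis, 12.2.7.1, 12.2.7.2 and 12.2.7.3, and carry the wording into the SAP:

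- Derive maximal change, ON status, time to ON, duration of ON and dyskinesia change only from assessments before the first anti-parkinsonian dose after study drug. Use data to 8 h if there is none, and to the existing 24 h limit for duration of ON.
- Count subjects dosed before turning ON as not ON, with time to ON not reached by 8 h and duration of ON zero. Otherwise end duration of ON at the first such dose, flagged as censored if the subject was still ON.
- Report the AUC over 0-4 h, cut at any earlier dose and divided by hours observed, beside the 8-hour AUC.
- Replace 12.2.7.2 with the all-ratings maximal change as the sensitivity analysis.
- Record the clock time of the first anti-parkinsonian dose for every subject, and tabulate use and timing by group and by route (non-response, or ON then OFF).
- Reconcile footnote 5 of Appendix 1 with the 8-hour observation rule, 6.1 with the Synopsis and 8.2 on medication after ON then OFF, and the Synopsis with 6.1 and 8.2 on resuming medication at 8 h. Which clinical rule applies is for the sponsor.

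The cost is wording. Medications after study drug are already collected on Day 1 (8.2) and listed on CRFs (9.8), so at most a clock-time field is new for subjects dosed within 8 h. One statistical cost remains: a subject dosed just after 4 h contributes 8 ratings instead of 12, which lowers the expected maximum by about 0.6 to 0.7 points. This is why the cut differences in step 3 sit up to 0.3 above the no-levodopa values.

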12.2.7.2 SENSITIVITY ANALYSIS OF THE PRIMARY EFFICACY ENDPOINT

No sensitivity analyses will be performed on the primary efficacy endpoint.

12.2.7.3 SECONDARY EFFICACY ANALYSES

The secondary endpoints consist of the following:

- Duration of ON time on Day 1
- Percentage of subjects that turn ON on Day 1
- Time to ON on Day 1
- Area under the curve for UPDRS Part III during the 8 hours of assessment on Day 1
- Change from pre-dose dyskinesia rating (from the UPDRS Part III motor response and dyskinesia assessment)

For continuous variables, descriptive statistics (n, mean, SD, median, minimum, and maximum) will be provided for actual values and changes from baseline to each time point. For categorical variables, subject counts and percentages will be provided. Summaries will be presented by treatment group. Graphical displays will be created as appropriate, including for the UPDRS by time point.

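### The mean/SD summary prescribed for continuous secondary endpoints does not suit time to ON, which has no value for subjects who never turn ON

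*Protocol*

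**What the plan says.** Protocol section 12.2.7.3 lists "Duration of ON time on Day 1", "Percentage of subjects that turn ON on Day 1" and "Time to ON on Day 1" as separate secondary endpoints. It then states how they are summarized: "For continuous variables, descriptive statistics (n, mean, SD, median, minimum, and maximum) will be provided for actual values", together with changes from baseline, and counts with percentages for categorical variables. It names no time-to-event summary and no value for a subject who never turns ON.

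Section 8.2 says of the measurements: "Time to ON and duration of ON, if applicable, will also be recorded". Section 6.1 sets the observation schedule: "every 30 minutes for 4 hours and then hourly for 4 additional hours (i.e., 8 hours total post-dose". For subjects still ON at the end of that window, section 6.1 extends follow-up of the ON period; those who "remain ON after 8 hours, should be called the next morning to record the time they turned OFF". There is no matching extension for subjects who have not yet turned ON.

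Section 8.2 also allows usual medication from 4 h in subjects with severe, unresponsive symptoms: "the subject's regularly scheduled levodopa dose and other anti-parkinsonian medications may be administered, if deemed necessary". Ratings continue to 8 h either way.

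Section 12.2.2.1 keeps every randomized, dosed subject with one post-baseline motor score in the mITT population, whether or not that subject turns ON.

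**The concern.** A separate endpoint for the percentage turning ON shows that some subjects are expected not to. For such a subject time to ON is not an ordinary missing value: all that is known is that it exceeds the observed window. A mean and SD cannot use that information. Applied as written, the rule in 12.2.7.3 gives a mean over those who turned ON, and turning ON is itself an outcome of treatment. The groups compared are then no longer the randomized groups, although the mITT definition keeps everyone.

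Two things follow. If active drug also turns slower subjects ON, its mean can equal or exceed the placebo mean while more of its subjects respond. And because placebo is small, its mean or SD may not exist. No formal comparison is planned, so these summaries are what the reader will have on speed of onset.

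**Working it through.** **Stated inputs.** Three cohorts of 8, randomized 6:2, give 3 × 6 = 18 active and 3 × 2 = 6 placebo subjects, 24 in all, as in the synopsis. Post-dose ratings: 8 half-hourly plus 4 hourly = 12, ending at 8 h. The protocol gives no ON rate, time to ON or duration, so it has no figure to reproduce. Every rate and time below is an assumption.

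**1. Can the placebo summary be computed?** Let p be the placebo ON rate. With all 6 placebo subjects pooled, the chance of no value is (1 − p)^6. The chance of at most one value, so no SD, is (1 − p)^6 + 6p(1 − p)^5. Within one cohort of 2 placebo subjects, the chance of at most one value is 1 − p².

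| p | no value (n = 6) | at most one (n = 6) | at most one (n = 2) |
|---|---|---|---|
| 10% | 53% | 89% | 99% |
| 20% | 26% | 66% | 96% |
| 30% | 12% | 42% | 91% |
| 50% | 2% | 11% | 75% |

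**2. A six-per-group example.** Placebo: 1 of 6 ON, at 1 h. Active: 4 of 6 ON, at 1, 2, 3 and 4 h.
- Mean among those ON: 1.0 v (1 + 2 + 3 + 4)/4 = 2.5 h. Active looks 1.5 h slower.
- 8-h restricted mean over all subjects: (1 + 5 × 8)/6 = 6.83 h v (1 + 2 + 3 + 4 + 2 × 8)/6 = 4.33 h. Active is 2.5 h faster.

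**3. Exponential times, closed form.** For ON hazard λ, the proportion ON by 8 h is F = 1 − exp(−8λ), the 8-h restricted mean is R = F/λ, and the mean among those ON is (R − 8(1 − F))/F.
- λ = 0.05/h: F = 33%, R = 6.59 h, mean among those ON 3.73 h.
- λ = 0.10/h: F = 55%, R = 5.51 h, mean among those ON 3.47 h.
- Differences: 3.73 − 3.47 = 0.26 h among those ON; 1.09 h over all subjects (from unrounded values). The summary among those ON keeps 0.26/1.09, about 24%.

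**4. Range over other assumptions.** ON rates, placebo v active: 10 v 50%, 20 v 50%, 20 v 70%, 33 v 67%. With all subjects kept, time to ON is pT + (1 − p)8 and duration is pD, where T and D are the means among those ON. For example, at 20 v 50% with T = 2 h in both groups: 0.2 × 2 + 0.8 × 8 = 6.8 h v 0.5 × 2 + 0.5 × 8 = 5.0 h, a difference of −1.8 h.

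| Assumption | Time to ON: ON-only v all | Duration: ON-only v all |
|---|---|---|
| A. Drug changes only the chance of ON (T = 2 h, D = 3 h in both groups) | 0 v −1.8 to −3.0 h | 0 v +0.9 to +1.5 h |
| B. Drug also acts among those ON (T 1.5 v 2 h, D 4 v 3 h, active v placebo) | keeps 15–24% | keeps 45–71% |
| C. Extra active responders turn ON later (T 2.0 v 1.5 h, active v placebo; D = 3 h in both) | +0.5 v −1.7 to −2.9 h (sign reversed) | 0 v +0.9 to +1.5 h |

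In every row the percentage turning ON still differs by 30 to 50 points.

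**The case against.** The strongest reply is that nothing here is fixed wrongly. The sentence in 12.2.7.3 goes on to changes from baseline at each time point, which fits UPDRS and dyskinesia ratings but not time to ON. Almost the same sentence serves the safety data in 12.2.8. Section 12.2.1 applies such statistics where nothing else is specified, and both that section and the synopsis point to a detailed SAP. A Kaplan-Meier curve is itself descriptive and could appear there without contradicting the protocol.

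This lowers the weight of the point but does not remove it. Time to ON is one of the listed endpoints, the only rule given for continuous variables is the unsuitable one, and an SAP that follows it literally inherits the problem.

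A reader might go further and infer that subjects never ON are dropped from both endpoints, so that the drug effect largely vanishes from the results. The documents do not support that:
- No exclusion is written. It follows from the arithmetic for time to ON. For duration, 0 h is a natural value that the text permits.
- The wording in section 8.2 about recording these measures where they apply concerns data collection, not analysis.
- The percentage turning ON, the maximal UPDRS Part III change and the 8-h UPDRS area under the curve do not depend on this rule and would still show an effect. The reported n and the listings would show how few values lie behind a mean.
- The size of any loss depends on ON rates and times that the protocol does not give.

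A further fair objection concerns the remedy. Censoring subjects when they take usual medication would be informative. Before 8 h section 8.2 offers that medication to subjects with severe symptoms and no response, so treating them as likely to turn ON as those who remain would inflate the proportion ON, most in the group with most non-responders. This stands, and the fix below avoids it.

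**Conclusion.** The point holds for time to ON. The stated summary, taken literally, covers only subjects who turned ON and can hide or reverse a difference. Under the assumed scenarios it keeps at most about 24% of the all-subject difference and at worst has the wrong sign. With 6 placebo subjects in total, the chance that no placebo SD can be computed is 11% to 89% for assumed placebo ON rates of 50% down to 10%.

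For duration of ON the point is weaker. The gap is an unstated value, and the share of the difference kept runs from 0% to 71% if subjects never ON are left out.

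No test or error rate is affected, and the percentage turning ON is a partial safeguard. It does not correct a mean time to ON that points the wrong way. The change is worth making before the SAP is finalized, but it concerns descriptive secondary endpoints and does not undermine the trial.

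**What to change.** In section 12.2.7.3, take time to ON and duration of ON out of the generic rule and state:

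- **Time to ON:** summarize over all mITT subjects, by treatment group, as the cumulative proportion ON at each of the 12 assessment times to 8 h. Add the median if it is reached, or the 8-h restricted mean.
- **Usual medication before ON:** for this analysis, count a subject who takes regular anti-parkinsonian medication before turning ON as not ON on study drug through 8 h. Do not censor at that medication. This is a counting rule only and leaves the conduct of Day 1 unchanged.
- **Duration of ON:** set to 0 h for subjects who never turn ON and keep them in the summary.
- **Supplement:** the mean and SD among those who turned ON may stay, labelled as restricted to that subset and shown with its n.

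The cost is a few sentences and slightly more analysis work, with no change to the assessment schedule. In groups this small the median may not be estimable; the proportion ON by time is then the main result.
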